# 8.3 Exploratory Endpoints

Exploratory endpoints for this study will be analyzed as follows:

**Endpoint 1:** A comparison of the stool consistency scores from the mothers on-study to re-scores from mothers not enrolled on-study based only on the uploaded images

Each mother on-study will score stool images based on consistency type compared to examples provided by the BITSS (Score 1 to 7). At End of Study for on-study mothers, images within the database will be sent to mothers who are not enrolled on-study for scoring based on the same BITSS criteria (Score 1 to 7). All scores are recorded as integers.

Inter-rater scores will be compared for agreement. Images in which the on-study mother's score was different from the non-enrolled study mother's scores will be flagged "disagree", while images where both mothers agree will be flagged as "agree". The magnitude of disagreement will be quantified by subtracting the non-study enrolled mother's score from the on-study mother's score. For example, if the on-study mother scored an image as a 6 and the non-enrolled mother scored the same as a five, we would consider the magnitude of disagreement as "-1". Conversely, if the on-study mother scored an image as 5 while the non-enrolled mother scored the same image as 6, the magnitude of disagreement would be "1".

Percent agreement will be tabulated for all BITSS categories (Score 1 to 7) based on the on-study mother's original score. Mean overall scores and mean overall differences between study groups (on-study and not enrolled on-study mothers) will be presented.

Scores between the two non-enrolled mothers will also be compared for agreement. Per comparisons with the on-study and each non-enrolled mother, images in which one of the non-enrolled mother's scores was different from the other non-enrolled study mother's scores will be flagged "disagree", while images where both mothers agree will

be flagged as "agree". The percent agreement and magnitude of agreement between the two non-enrolled mothers will also be quantified, using non-enrolled mother #1 as the referent.

**Endpoint 2:** An assessment of mothers' perceptions of the usability of the stool scoring process

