#### 8.5 Tables, Figures, and Lists

#### 8.5.1 BITSS Score Comparison

Tables of outputs from the proposed analysis are detailed in the TLF Deliverable Shell (see Section 10.2 for details).

Tables 1a-b provide the agreement between on-study mothers' BITSS scores and non-enrolled mothers' re-scores of the same images. Conceptually, the first column provides the on-study mother's scores. As on-study mothers will only be able to record integer scores ranging from 1-7, only these scores are listed in Column 1. Column 2 describes the number of unique subjects, e.g. on study mothers who reported BITSS scores. Column 3 enumerates the quantity of images collected for each score. Column 4 provides the overall and score-based percent agreements. Percent agreement is defined as the percentage of time the non-enrolled mother (mother #1 and mother #2 for Tables 1a and 1b, respectively) agreed with the onstudy mother's score. Column 5 depicts the mean score for the non-enrolled mother. The mean level of disagreement (Column 6) is defined as the average of the magnitude to which non-enrolled mothers disagreed when disagreements occurred.

Table 1c describes the agreement between the two non-enrolled mothers in similar format: Column 1 provides the scores of non-enrolled Mother #1; Column 2 describes the number of unique subjects (on-study mothers) for which the non-enrolled mothers were assigned to re-score; Column 3 quantifies the number of images; Columns 4 describes the percent agreement between the two non-enrolled study mothers; Column 5 depicts the mean score of non-enrolled mother #1 and non-enrolled mother #2, quantified by the mean level of disagreement using mother #1 as the referent.

Individuals graphs will be created for each mother that plot each of the nonenrolled mother's scores across the BITSS range as reported by on-study mothers (as represented by values on x-axis; Figures 1a-1b). Points will be plotted for each comparison score from the non-enrolled mother (y-axis). The BITSS scores of the two non-enrolled mothers will also be compared against each other in a separate graph (Figure 1c). If an on-study mother does not submit an image for a given score,

no comparisons can be made through non-enrolled mothers. Therefore, no points will be plotted in such cases.

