A Spearman correlation coefficient and p-value will be calculated to measure the level to which a non-enrolled mother agreed with each individual on-study mother (Figure 1a-b) or the other non-enrolled mother (Figure 1c). In Figures 1a-b, a p-value of 0.05 will indicate that the on-study mother's judged scores were significantly correlated with the non-enrolled mother's re-scores. In Figure 1c, a p-value of 0.05 will indicate that non-enrolled mother #1's re-scores were significantly correlated with the non-enrolled mother #1's re-scores.

A bubble plot will also be created to graphically represent the level of agreement between on-study and non-enrolled mother (Figures 2a-2b) and between the two non-enrolled mothers (Figure 2c). A greater correlation will be represented by a larger bubble, while a lesser correlation will be represented by a smaller bubble.

Both the individual graphs' and bubble plots' final format will be in accordance with the agreed upon TLF Deliverable Shell submitted with the final version of this SAP. The number of individual graphs is set at 100 within the TLF Deliverable Shell; however, this number may vary depending on the number of participants included in the final database.

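### SAP 8.5.1 measures agreement by correlation in Figures 1a–c and 2a–c, although SAP 8.3 defines agreement as an identical score (exploratory endpoint)

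*SAP*

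**What the plan says.** SAP 8.3 works image by image with integer scores from 1 to 7. "Images in which the on-study mother's score was different from the non-enrolled study mother's scores will be flagged" as disagreements, and images on which both mothers agree are flagged as agreements. Agreement therefore means the same score on the same image. The summary follows from that: "Percent agreement will be tabulated for all BITSS categories (Score 1 to 7) based on the on-study mother's original score". SAP 8.5.1 carries it into Tables 1a–b, where "Column 4 provides the overall and score-based percent agreements", and Table 1c does the same for the two re-scorers.

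The figures in SAP 8.5.1 use something else. "Individuals graphs will be created for each mother that plot each of the nonenrolled mother's scores across the BITSS range", with 100 such graphs planned in the TLF Deliverable Shell. For these, "A Spearman correlation coefficient and p-value will be calculated to measure the level to which a non-enrolled mother agreed with each individual on-study mother"; the same statistic serves Figure 1c. On the test, "a p-value of 0.05 will indicate that the on-study mother's judged scores were significantly correlated with the non-enrolled mother's re-scores". For Figures 2a–b, "A bubble plot will also be created to graphically represent the level of agreement between on-study and non-enrolled mother", and Figure 2c does this for the two re-scorers. Bubble size increases with correlation; the coefficient and the plotting unit are not named.

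**The concern.** One word, agreement, covers two different quantities under the same endpoint. Rho responds to rank order. It ignores a constant shift, and it depends heavily on how many distinct scores an infant's stools receive. A reader who takes the Figure 1 or Figure 2 summary as agreement in the SAP 8.3 sense can therefore be misled in either direction.

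What is at stake is modest. Tables 1a–c pool mothers within each score, so in the SAP text the per-mother graphs are the only mother-by-mother view of agreement, and rho with its p-value is the only number attached to them. The risk is a wrong impression of how closely individual mothers' scores match the re-scores, not a wrong primary result.

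**Working it through.** The plan gives no expected rho, agreement rate or sample size for this comparison, so there is no figure to reproduce. From the SAP: integer scores 1–7, agreement as an identical score (8.3), Spearman's rho and a 0.05 threshold (8.5.1). All score patterns, error rates and image counts below are assumptions, not trial data; 15, 30 and 60 images correspond to a stool every other day, one a day and two a day for 30 days.

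**1. Constant shift.** On-study scores 1 to 6, five images each (n = 30); the re-score is always one higher. The two rank orders are identical, so rho = 1.00. Exact agreement is 0/30 = 0%. With 200 images at each of scores 1–7 and the shift capped at 7, rho = 0.99 and agreement = 200/1,400 = 14.3%.

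**2. Narrow range.** Thirty images: 28 scored 4 by both mothers, one scored 4 then 5, one scored 5 then 4. With two values per rater, rho reduces to

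(0 − 1/30 × 1/30) / (1/30 × 29/30) = −1/29 = −0.03 (p = 0.86),

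while agreement = 28/30 = 93%. If both mothers score all 30 images 4, rho is undefined and agreement is 100%.

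**3. Partial errors.** Simulated mothers, 30 images each, with an error of one category on 20% or 80% of images. Mean rho:

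| Score mix | All errors +1: 20% v 80% | Errors ±1 at random: 20% v 80% |
|---|---|---|
| Even over 1–6 | 0.97 v 0.97 | 0.97 v 0.88 |
| 50/25/15/10 | 0.91 v 0.91 | 0.90 v 0.71 |
| 25/50/25 | 0.87 v 0.87 | 0.86 v 0.59 |
| 10/80/10 | 0.71 v 0.71 | 0.69 v 0.40 |

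- With +1 errors, agreement averages 80% v 20%, mean absolute difference is 0.20 v 0.80, and p < 0.05 in at least 99% of runs. For the even mix, rho is also 0.97 v 0.97 at 15 and 60 images.
- The equal rhos follow from the one-directional assumption: +1 on 80% of images is a constant +1, which rho ignores, combined with −1 on the other 20%.
- With ±1 errors, rho does fall as errors rise, but it is still not on the agreement scale. A rho of 0.69 goes with a 20% error rate (10/80/10 mix), and a higher rho of 0.88 goes with an 80% error rate (even mix). In the even mix, capping at 1 turns some errors back into matches, so agreement at the 80% rate is 0.20 + 0.80 × 1/6 × 1/2 = 27%.

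**4. What the p-value tests.** Smallest rho with two-sided p < 0.05 (sidedness is not stated in the SAP): t/√(n − 2 + t²). At n = 30, t = 2.048, giving 2.048/√(28 + 4.19) = 0.36. The same formula gives 0.51 at n = 15, 0.25 at n = 60, and 0.05 if 1,400 images were pooled in Figure 1c. Passing the threshold shows only that rho is not zero.

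**5. Why the tables do not fill the gap.** If 50 mothers agreed on 80% of images and 50 on 20%, with equal image counts, the pooled figure would be (80% + 20%)/2 = 50%. It would not show the two groups.

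**The case against.** The strongest case for the plan is that agreement is already handled. SAP 8.3 and Tables 1a–c give percent agreement, the magnitude of disagreement and the comparison of the two re-scorers. The interim output in SAP 8.4 consists of those three tables and no correlation figure. No objective asks for a ranking of mothers, and nothing is decided on rho. Figures 1a–c also plot the score pairs, so a constant shift would show as points off the diagonal. All of this stands, and it limits the weight of the point. It does not make rho a measure of what SAP 8.5.1 says it measures.

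Stronger readings that a reader might infer, and that the documents do not support:

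- *That the SAP treats p = 0.05 as proof of agreement.* The p-value sentences speak only of significant correlation, which is accurate. The fault lies in the sentence that states the purpose of the statistic and in the description of the bubble plots.
- *That Figures 2a–c use Spearman's rho.* Spearman is named only for Figures 1a–c. The objection applies to any correlation, but the coefficient for the bubbles is simply not stated.
- *That rho can never tell a well-matched mother from a poorly matched one.* This holds for errors in one direction. With errors in both directions, rho does separate them within a given score mix.
- *That overlapping integer points will hide partial shifts on the graphs.* This depends on jitter or counts, which belong to the TLF Deliverable Shell. That shell is not among the documents.
- *That a rank correlation has no place here.* SAP 11 limits the evaluation to descriptive analyses but includes comparisons of trends, so reporting rho as association is defensible.

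**Conclusion.** Wrong as written, at low to moderate priority and for the exploratory endpoint only. SAP 8.5.1 assigns correlation to a purpose that SAP 8.3 defines as identical scoring. The mismatch can be complete in either direction: rho 1.0 at 0% agreement, and rho −0.03 or undefined at 93% or 100% agreement. These cases follow from the definition of rho and need no assumption about error rates, although how often such patterns would occur in the trial is unknown. The simulated comparisons (0.97 v 0.97 with one-directional errors; 0.97 v 0.88 down to 0.69 v 0.40 with errors both ways) do rest on assumed mixes, error rates and 30 images per mother. Tables 1a–c and the primary image count are unaffected.

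**What to change.** - In SAP 8.5.1, describe rho as rank association, not agreement, and state that its p-value is not evidence of agreement. Dropping the p-value altogether is a matter of preference.
- On each per-mother graph and on Figure 1c, print the number of images, percent exact agreement, signed mean difference and mean absolute difference. State the direction of the signed difference: the SAP 8.3 rule (on-study minus re-score) gives 6 − 5 = +1, while its worked example gives −1. That conflict is a separate matter, but it has to be settled before a signed value is printed.
- In Figures 2a–c, size the bubbles by number of images per score pair or by percent exact agreement, and record the choice in the TLF Deliverable Shell.
- Weighted kappa per rater pair is optional. It also depends on the score mix, so it should be read beside percent agreement.

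The cost is wording in the SAP and the shell plus a few lines of code; no new data are needed. The drawback is imprecision for a single mother: 15 of 30 images gives a 95% Wilson interval of 0.5 ± 0.98/√(30 + 1.96²), or 33% to 67%. The image count must therefore stand beside each percentage.

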# 7.2 End of Study

At the end of the study, the mother will be asked to complete an eQuestionnaire to assess and comment on the usability of the ClaimIt app and the scoring process (Appendix I).

Also, the Sponsor will identify two mothers who were not enrolled in the study. They will be provided a collection of uploaded study images and asked to re-score each image according to the BITSS.

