#### 8 Statistical Analysis

#### 8.1 Sample Size Calculations

The primary objective of this study is to create a database with 200 images with stool per each score (BITSS types 1 to 7) and 200 images of empty (no stool) disposable diapers. The sample size of 100 subjects with an approximate withdrawal rate of 15% was predetermined, and therefore, a formal sample size calculation was not performed.

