## **11 Study Limitations**

This is an exercise in collecting images for a database using the ClaimIt platform accompanied by a participant feedback questionnaire. As such, the study's ability to draw any statistical inferences is limited.

Inclusion criteria for this study may introduce biased sampling as participation is limited to subjects with access to reliable in-home internet and a mobile technology to accommodate the ClaimIt App. Furthermore, although the study instruments are based on a validated scoring tool, self-reported stool scores are subjective and not based on clinical evaluation. Finally, as the sample size was predetermined without a formal power calculation, the statistical evaluation was restricted to descriptive analyses with data visualizations of subjective measures and trends comparisons. However, this study provides proof of concept and utility of a digital clinical assessment.

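### SAP 8.5.1 puts a 0.05 significance verdict on each mother's correlation although SAP 11 limits the evaluation to description, and that verdict depends on image count and score spread, not on agreement alone

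*SAP*

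**What the plan says.** SAP 8.5.1 describes one graph per on-study mother, plotting a re-scorer's BITSS scores against hers (Figures 1a-b, one figure per re-scorer). It then states: "A Spearman correlation coefficient and p-value will be calculated to measure the level to which a non-enrolled mother agreed with each individual on-study mother". The interpretation rule follows: "In Figures 1a-b, a p-value of 0.05 will indicate that the on-study" mother's scores and the re-scores are significantly correlated. A parallel sentence covers the two re-scorers against each other (Figure 1c). Sidedness, a minimum number of images per mother, the handling of constant scores and any multiplicity adjustment are not given.

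On scale, SAP 8.5.1 says: "The number of individual graphs is set at 100 within the TLF Deliverable Shell", adding that this may vary with the final database. SAP 7.2 says that "the Sponsor will identify two mothers who were not enrolled in the study".

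On the status of the analysis, SAP 8.1 says that "a formal sample size calculation was not performed". SAP 11 gives that as the reason why "the statistical evaluation was restricted to descriptive analyses with data visualizations of subjective measures and trends comparisons", and describes the study's capacity for statistical inference as limited.

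Separately, SAP 8.3 flags each image as agree or disagree, and SAP 8.5.1 defines percent agreement for Tables 1a-b, by score and overall.

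**The concern.** There are three strands, in order of weight.

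1. **Wrong null for the question.** Exploratory endpoint 1 asks whether re-scorers agree with on-study mothers. Two people looking at the same stool can be expected to correlate to some degree, so a small p-value says little about whether they chose the same type.
2. **The verdict depends on things other than agreement.** Each test uses one mother's images. Their number is not fixed, because every bowel movement is photographed over 30 days or longer, and the spread of scores differs between infants. Two mothers with the same agreement can receive opposite verdicts.
3. **Inconsistency with SAP 11.** A rule that turns p-values into statements of significance is inferential, and the SAP elsewhere says that the evaluation is descriptive.

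What is at stake is how Figures 1a-b are read. A graph without a significant result would look like poor scoring when the cause may be few images or an infant with little variation in stool type.

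**Working it through.** **Plan's own figures.** The 100 subjects were predetermined, so there is no alpha, power or effect size to reproduce. The image target does reproduce: 7 × 200 + 200 = 1600.

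**Inputs from the documents.** Threshold 0.05 (SAP 8.5.1, read here as p ≤ 0.05); about 100 on-study mothers (SAP 8.5.1), or 85 if the 15% who withdraw contribute nothing (SAP 8.1); two re-scorers (SAP 7.2); at least 1400 stool images (SAP 4).

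**Assumptions.** Two-sided tests. Images per mother are not stated. The database minimum implies an average of at least 1400 / 100 = 14, and one stool a day for 30 days would give 30. A range is therefore shown.

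**Step 1: what the threshold demands.** The smallest |rho| called significant is approximately t / √(n − 2 + t²), with t the 0.975 quantile on n − 2 degrees of freedom. For n = 14, t = 2.179, so 2.179 / √(12 + 4.748) = 0.532.

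| Images | 6 | 10 | 14 | 30 | 60 | 100 |
|---|---|---|---|---|---|---|
| Critical \|rho\| | 0.81 | 0.63 | 0.53 | 0.36 | 0.25 | 0.20 |

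The same observed rho of 0.50 gives p = 0.069 with 14 images and p = 0.005 with 30.

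**Step 2: same agreement, different verdict.** Assumed rater model: the re-score equals the mother's score with probability 0.7 and is otherwise one type higher or lower, held within 1 to 7. Two infants are compared:

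- Narrow: scores 6 and 7 with probabilities 0.7 and 0.3. Because a 7 cannot move up, exact agreement is 0.7 × 0.70 + 0.3 × 0.85 = 0.745.
- Wide: scores 1 to 7 in equal shares. Exact agreement is 0.70 + (2/7) × 0.15 = 0.743.

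Share of simulated mothers called significant (thousands of mothers per setting; repeat runs agree within about two percentage points):

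| Images | 6 | 10 | 14 | 30 | 60 |
|---|---|---|---|---|---|
| Narrow (6 and 7) | 28% | 53% | 73% | 98% | 100% |
| Wide (1 to 7) | 95% | 100% | 100% | 100% | 100% |

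In the narrow case about 13% of six-image sets have no coefficient, because one rater's scores are constant. They count as not significant in the 28%. Among sets with a coefficient the share is about 31%.

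**Step 3: is it peculiar to extreme stools?** Scores 1 and 2 only give about the same shares as 6 and 7. Scores 4 and 5 only, at 70% agreement because there is no truncation, give about 27% with 6 images and 56% with 10. Four equally frequent scores (3 to 6), also at 70%, give 82% and 98%. The driver is range, not position on the scale.

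**Step 4: a less accurate re-scorer.** With agreement near 50% and errors of one or two types, an infant with 80% of stools of one type is called significant in 25% of cases with 14 images, 54% with 30 and 94% with 90. For widely spread scores the figures are 93%, 100% and 100%.

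**Step 5: correlation against agreement.** A re-scorer who is always exactly one type higher gives rho = 1 with 0% agreement.

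**Step 6: number of tests.** 100 × 2 = 200, or 85 × 2 = 170. If every true rho were zero, 200 × 0.05 = 10 (or 170 × 0.05 = 8.5) would be significant by chance.

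**The case against.** **The conflict with SAP 11 is mild.** SAP 11 calls inference limited rather than absent, allows comparison of trends, and already warns the reader. This is fair, but a rule for declaring significance still goes beyond a descriptive evaluation.

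**Nothing depends on the verdict.** The endpoint is exploratory. No image is excluded or relabelled, and Tables 1a-b report percent agreement by score with image counts. This stands, and it limits the importance of the point. It does not make the verdict informative.

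**Image counts may be adequate.** One stool a day for 30 days gives 30 images, and mothers of infrequent stoolers may be asked to continue. With 30 images the narrow case in Step 2 reaches 98%. This stands in part: extension is voluntary, no minimum is set, and Step 4 shows the problem persisting at 30 images when agreement is lower.

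**Stronger readings that a reader might infer.**

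- *Mothers of infants with hard or liquid stools will look like worse scorers.* Not supported: Step 3 shows nearly the same result for scores 4 and 5, and Tables 1a-b are where agreement by stool type is reported.
- *Image count alone decides the verdict.* Not supported: score spread matters at least as much.
- *About 10 of 200 results will be false positives.* This requires zero true correlation for every pair, which is not credible for two people scoring the same pictures. The count of 170 to 200 is itself derived rather than stated.
- *The SAP will mark mothers as not significantly correlated.* It never says this; it states only what a p-value of 0.05 indicates.

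**Conclusion.** The concern holds, as a point about interpreting Figures 1a-b. The 0.05 rule does not fit the descriptive status that SAP 11 declares, it tests a null that does not address agreement, and its outcome moves with image count and score spread. At about 74% exact agreement the chance of a significant verdict runs from about 28% (6 images, scores 6 and 7 only) to about 95% (6 images, scores spread over 1 to 7). At the implied minimum average of 14 images the contrast is 73% against 100%; at 30 images it nearly closes under that model.

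These percentages rest on an assumed rater model, assumed score distributions and assumed images per mother. The direction follows from the critical values in Step 1 and the comparison of score ranges, and does not need those exact figures. Multiplicity, at about 170 to 200 unadjusted tests, is secondary.

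The change should be made, but the primary image-count endpoint and the agreement tables are untouched.

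**What to change.** In SAP 8.5.1 and the figure shell:

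- For Figures 1a-b, delete the p-value and the sentence that interprets 0.05.
- Print on each graph the number of images and the percent agreement. SAP 8.5.1 already defines the measure and SAP 8.3 supplies the agree/disagree flag; the only addition is to calculate it per mother.
- If the coefficient is kept as a description, show none where one rater's scores are constant.
- For consistency with SAP 11, delete the Figure 1c p-value and its sentence too, since rejecting zero correlation does not show agreement there either. The per-mother image-count and multiplicity arguments do not apply to Figure 1c.

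Adjusting the threshold instead would not solve the problem. Bonferroni over 200 tests is 0.05 / 200 = 0.00025, which needs |rho| of at least 0.829 with 14 images and 0.621 with 30, so the verdict would still depend on image count.

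The cost is SAP and figure-shell wording, with no new data and slightly less programming.
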